## **8.9 Health Economics**

Health Economics/Medical Resource Utilization and Health Economics parameters are not evaluated in this study.

## 9.0 STATISTICAL CONSIDERATIONS

### 9.1 Statistical Hypotheses

Formal statistical hypothesis testing is not planned for this study. All analyses will be considered exploratory and descriptive.

### 9.2 Sample Size Determination

The study will enroll up to a maximum of 63 subjects who will be randomized into dose escalation cohorts. The sample size is not based on statistical considerations but is typical for studies of this nature and is considered adequate to characterize the distribution of the planned endpoints. Any statistical testing will be considered exploratory and descriptive.

### 9.3 Populations for Analyses

For purposes of analysis, the analysis sets are defined in Table 11.

**Table 11 Analysis Sets**

Analysis Set	Description
Safety Evaluation Population	All subjects randomly assigned to the IP and who take at least 1 dose of IP. Subjects will be analyzed according to the treatment they received.
Dose-limiting Adverse Event (DLAE) Evaluation Population	All subjects who received at least 1 dose of IP and completed the 15-day DLAE follow-up period.
Pharmacokinetic (PK) Evaluation Population	All subjects who received at least 1 dose of IP and have at least 1 quantifiable IP plasma concentration collected postdose without important protocol deviations/violations or events thought to significantly affect the PK results.
Exploratory Pharmacodynamic (PD)/Biomarker Evaluation Population	All subjects who take at least 1 dose of IP and have at least 1 exploratory PD variable or biomarker endpoint collected postdose without important protocol deviations/violations or events thought to significantly affect the PD results.

### 9.4 Statistical Analyses

The SAP will be developed and finalized before database lock and will describe the subject analysis sets to be included in the analyses, and procedures for accounting for missing, unused, and spurious data. This section focusses on the summary of the planned statistical analyses of the primary and secondary endpoints.

All analyses, summaries, and listings will be performed using SAS® software (EG 7.23 or higher). Results will be summarized by treatment and overall, where appropriate. Subjects who received placebo will be combined into 1 treatment group for purposes of analysis. Change from baseline will be calculated as value postdose subtracted by value at baseline. The baseline measure will be defined as the last non-missing measure prior to initiation of IP.

The following descriptive statistics will be used as applicable to summarize the study data unless otherwise specified:

- Continuous variables: sample size (n), mean, standard deviation (SD), median, minimum (min), and maximum (max).
- Summaries for JK07 concentrations will include the coefficient of variation and PK parameter summaries will also include the geometric mean (except for  $t_{max}$  which will only be presented as min, median, max).
- Categorical variables: frequencies and percentages.

Individual subject data will be presented in listings.

#### **9.4.1 Efficacy Analyses**

See [Section 9.4.4](#) for assessment of exploratory efficacy analyses.

#### **9.4.2 Pharmacokinetic/Pharmacodynamic Analyses**

##### **PK Analysis:**

JK07 concentrations derived from the validated assay, concentration ratios, and calculated parameters will be listed and descriptively summarized by active treatment for the PK population (subjects who have received JK07 and do not have any protocol deviations/events which may affect the PK results). JK07 serum concentration-time profiles will be graphically displayed by treatment on linear and semilogarithmic scale for each assay, as appropriate. Scatter plots of individual values and geometric means of PK parameters, area under the plasma concentration-time curve from time zero extrapolated to infinity ( $AUC_{(0-\infty)}$  [or area under the plasma concentration-time curve from time zero to the time of the last quantifiable concentration ( $AUC_{(0-\text{last})}$ ) if  $AUC_{(0-\infty)}$  is not calculable in most subjects]),  $C_{\max}$  as well as dose-normalized exposure parameters versus dose will be presented.

Dose proportionality of PK parameters such as  $C_{\max}$  and  $AUC_{(0-\infty)}$  [or  $AUC_{(0-\text{last})}$  if  $AUC_{(0-\infty)}$  is not calculable in most subjects] over the administered dose range may also be explored using a power model.

Further details will be presented in the SAP.

##### **Exploratory Exposure-Response Analysis:**

An exploratory evaluation of a plasma concentration to QT (C-QT) relationship will be conducted using a linear mixed effects model, with the drug-free-corrected (Day -1-corrected) change from baseline in QTcF as the response variable, denoted as  $\Delta QTcF$ . Independent variables will include the fixed effects time-matched JK07 plasma concentration obtained on Day 1, treatment indicator (treatment = 1 for subjects receiving JK07, and 0 otherwise), time point as a categorical variable, and random effects subject and time-matched JK07 plasma concentration obtained on Day 1. The analysis will be performed for the exploratory PD/biomarker population. Figures for mean time-matched change from baseline QTcF values versus JK07 mean concentrations (time-matched with QTcF) on Days 1 will also be generated. Hysteresis will be examined via by-subject hysteresis plots. Departures from a linear relationship will be examined graphically, and additional C-QT relationships other than the linear relationship may be explored if supported by data. A detailed plan of this analysis will be presented as part of the statistical analysis plan. The results for the C-QT analysis will be included in the CSR for this study. Further details will be presented in the SAP.

Exposure-response relationships may also be explored for safety and/or biomarker endpoint. Details regarding these analyses will be provided in the SAP.

Pharmacokinetic data from this study may be pooled with data from other future study(ies) and analyzed using population modeling approaches or used to explore exposure-response relationships. If performed, separate analysis plan(s) will be prepared; results from these analyses will not be part of the clinical study report.

#### **9.4.3 Safety Analyses**

All safety analyses will be performed on the Safety Population.

All safety data will be listed according to treatment group, subject number, and visit.

The AEs are defined in [Section 8.3.1](#). The DLAE are defined in [Section 4.6](#).

AEs will be coded using the Medical Dictionary for Regulatory Activities (MedDRA) Version 22. The number of AEs and incidence rates will be tabulated by preferred term and system organ class.

The AEs will be coded by maximum severity, relationship to study treatment, as SAEs or DLTs as needed, and will be categorized and tabulated for each treatment group (cohort).

DLAEs will be presented in the same manner as the AEs.

Incidence of injection site reactions will be summarized by treatment group, and if appropriate by assessment time.

All laboratory test results, vital signs measurements, ECG results, weight, and body mass index will be summarized for each treatment group using descriptive statistics at each visit for raw numbers and change from baseline. The incidence of treatment-emergent abnormal laboratory, vital sign, and ECG values will also be summarized using descriptive statistics.

For 12-lead ECG parameters (HR, PR, QRS, QT, QTcF), the 90 % confidence interval will also be presented for each parameter mean and change from baseline values. Outliers for QT and QTcF defined under outcome measures will be summarized using counts and percentages by treatment and sampling time, if appropriate and using subject-level maximum over time by treatment. The following categories will be presented by treatment and overall, for JK07:

- outlier QT and QTcF intervals (450-480 ms, 480-500 ms and >500 ms)
- change from baseline in QT and QTcF intervals (30-60 ms and >60 ms)

Additional corrections to QT may also be similarly analyzed. If relevant, analysis excluding ECGs capturing paced beats will be performed.

Abnormal findings on 12-lead ECG will be summarized by treatment using descriptive statistics.

All recorded ECGs will be interpreted on site and subsequently collected, digitized, and sent for central laboratory standardized measurements. The incidence (number of subjects and percent) of a confirmed positive ADA response will be summarized by treatment. The incidence of neutralizing anti-drug antibody response will also be summarized, if appropriate.

All data will be provided in data listings sorted by treatment group, subject number, and visit.

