10. Cerebrovascular accident or hospitalizations for CV (cardiovascular) causes other than routine percutaneous procedures such as device, battery, generator changes or pacemaker lead insertion/replacement, including HF, chest pain, stroke, transient ischemic attack, or arrhythmias within 2 months prior to screening.
11. Subjects at screening have an abnormal or clinically significant 12-lead ECG abnormality, that, in the opinion of the Investigator, would affect efficacy or safety evaluation or place the subject at risk.
12. History or evidence of clinically significant arrhythmias uncontrolled by drug therapy or use of an implantable defibrillator, long QT syndrome, or evidence of QT prolongation with QTcF >450 ms for males or QTcF >470 ms for females during screening and/or prior to randomization.
13. Clinically significant renal dysfunction as measured by the estimated glomerular filtration rate of <45 mL/min/1.73m^2 as calculated by local laboratory standards (Cockcroft-Gault equation for estimation of creatinine clearance [CrCl] [Cockcroft and Gault. 1976]) at screening, or a clinically significant change in renal function between screening and baseline.
14. Clinically significant liver dysfunction as measured by: ALT >2.0 × the upper limit of normal (ULN), alkaline phosphatase > 2.0 × ULN, AST >2.0 × ULN, or GGT >2.0 × ULN or serum bilirubin ≥ 1.2 × ULN at screening, or a clinically significant change in liver function between screening and baseline.
15. Subjects with alteration of the coagulation panel (international normalized ratio [INR]) and/or prothrombin time (PT) ≥1.5 × the ULN; activated partial thromboplastin time (aPTT) ≥1.5 × ULN, or serum albumin ≤3 gm/dL. For subjects on warfarin or other anticoagulants, an INR (or PT) considered by the Principal Investigator as therapeutically appropriate will be allowed.
16. Subjects with values of total CPK and/or CK-MB >2.5x ULN per institutional standards at screening.

17. Any subject who by Investigator's judgement, has a significant hematuria or proteinuria at screening.
18. Concurrent treatment with Class Ia or III antiarrhythmic drugs (the medication must have been discontinued more than 2 months before informed consent).
19. Positive screening for human immunodeficiency virus antibodies, hepatitis B surface antigen, or hepatitis C virus antibodies.

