Any emergent laboratory abnormality (e.g., clinical chemistry or hematology) or other abnormal assessment findings (e.g., ECG or vital signs) that meets any of the following criteria should be recorded as an AE or SAE:

- Associated with clinical signs and/or symptoms
- Requires medical or surgical intervention
- May require a change in current therapy, and leads to study treatment discontinuation, delay, or interruption
- Otherwise clinically significant as determined by the Investigator

Whenever possible, the clinical diagnosis, rather than the laboratory result, should be reported by the Investigator (e.g., anemia versus low hematocrit).

Emergent and clinically significant abnormal laboratory values occurring during the study will be followed until repeat tests return to normal, stabilize, or are no longer clinically significant.

Laboratory abnormalities that are not deemed clinically significant by the Investigator should not be reported as AEs.

All deaths that occur during the protocol-specified AE reporting period, regardless of attribution, will be recorded on an eCRF and SAE report form, and expeditiously reported to the Sponsor. This includes death attributed to progression of disease.

- When recording a death on an eCRF or SAE Report Form, the event or condition that caused or contributed to the fatal outcome should be recorded as the single medical concept.
- Death is an outcome of an event. The event that resulted in death (e.g., sepsis, stroke, myocardial infarction, etc.) should be recorded in the eCRF and reported on the SAE report form.
- If the death is attributed to progression of disease, record “disease progression” as the SAE term on the SAE Report Form.
- The term “unexplained death” should be captured if the cause of death is not known. However, every effort should be made to capture the established cause of death, which may become available later on (e.g., after autopsy).

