### **C. Sample Size**

Approximately 8 investigators and study centers are expected to participate in this study. A maximum of 63 subjects will be enrolled in the dose escalation cohorts. Five dose cohorts are planned. Two additional cohorts may be added as per the Data Review Committee (DRC) recommendation (total up to 7 cohorts) to receive IP.

For this study, no prospective calculations of statistical power have been made. The sample size is not based on statistical considerations but is typical for studies of this nature and is considered adequate to characterize the distribution of the planned endpoints. Any statistical testing will be considered exploratory and descriptive.

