### **C. Clinical Laboratory Results**

Laboratory test results include hematology; chemistry (including serum glucose on the Fingerstick Glucose Multi - Local form in the CRF); coagulation, urinalysis, analyzed by the local labs and collected in the EDC system. The severity of laboratory abnormalities will be graded using the CTCAE whenever possible.

Summaries of actual values and changes from baseline will be summarized descriptively by treatment group and overall for each scheduled visit and each timepoint where applicable.

For all laboratory tests, shift tables summarizing the Principal Investigator’s assessment of abnormality – i.e. Normal, Abnormal Clinically Significant (CS), Abnormal Non-Clinically Significant (NCS) – will be displayed. The counts and percentages of subjects who were normal at baseline and became abnormal subsequently, or the opposite, will be presented.

All laboratory test results will be presented in by-subject listings, with collection date, result and unit, normality and clinical significance, change from baseline, and the CTCAE grading wherever possible, at each visit and timepoint (where applicable). Abnormal results will be presented in a separate listing.

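### SAP VII.C lists CTCAE grades for laboratory values but names no table of them, so a grade rise from an abnormal baseline that stays within one investigator rating is in no laboratory count

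*Protocol*

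**What the plan says.** Protocol 9.4.3 (Safety Analyses) states: "The incidence of treatment-emergent abnormal laboratory, vital sign, and ECG values will also be summarized using descriptive statistics". Neither document defines treatment-emergent abnormality for a laboratory value.

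SAP VII.C (Clinical Laboratory Results) specifies four outputs:

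- Descriptive statistics of values and changes from baseline, by treatment group, visit and timepoint.
- Shift tables of the Principal Investigator's "assessment of abnormality – i.e. Normal, Abnormal Clinically Significant (CS), Abnormal Non-Clinically Significant (NCS) – will be displayed".
- Counts from those ratings: "The counts and percentages of subjects who were normal at baseline and became abnormal subsequently, or the opposite, will be presented".
- By-subject listings that show "normality and clinical significance, change from baseline, and the CTCAE grading wherever possible", plus a separate listing of abnormal results.

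SAP VII.C also says that abnormalities are graded by CTCAE where possible. The listing is the only output in that section that carries the grade.

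Abnormal baselines are eligible. Exclusion criterion 14 (Protocol 5.2) removes liver enzymes only above twice the upper limit, for example "AST >2.0 × ULN, or GGT >2.0 × ULN or serum bilirubin". Inclusion criterion 7 (Protocol 5.1) accepts hemoglobin from 9.0 g/dL.

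On adverse events, Protocol 8.3.7 says: "Laboratory abnormalities that are not deemed clinically significant by the Investigator should not be reported as AEs".

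**The concern.** A shift in an investigator's rating is not a shift in severity. A subject who starts above the reference range and then rises several-fold is abnormal before and after. If the rating does not change, the subject adds nothing to the normal-to-abnormal count and sits on the diagonal of the shift table. The CTCAE grade would separate this subject from one with a trivial excursion, but it is left in a listing.

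This matters because laboratory change from baseline is a primary endpoint, and emergent Grade 3 or higher hematologic, hepato-cellular or renal toxicity is a DLAE criterion (Protocol 4.6). The nonclinical sections give reason to watch these analytes: mild ALT, AST and/or GGT elevations in 2 of 10 JK07-treated monkeys (Protocol 2.2), and heart and/or kidney effects at 10 mg/kg and above in the single-dose monkey study (Protocol 2.3). The ratings come from investigators at about 8 centers, so a count built on them can vary with the rater as well as with the drug.

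**Working it through.** The plan gives no figure to reproduce. The check compares the texts and counts cells and visits.

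**1. What the shift table can show.** Three ratings at baseline by three after gives 3 × 3 = 9 cells.

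| Cells | Number | In the counts SAP VII.C names? | Visible in a full three-level shift table? |
|---|---|---|---|
| Normal→NCS, Normal→CS, NCS→Normal, CS→Normal | 4 | Yes | Yes |
| NCS→CS, CS→NCS | 2 | No | Yes |
| Normal→Normal, NCS→NCS, CS→CS | 3 | No | Only as no change |

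A grade rise inside NCS→NCS or CS→CS cannot be seen in any version of this table.

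**2. One subject traced through the outputs (illustrative).** GGT is 1.8 × ULN at baseline, which is eligible, and is rated NCS. It rises several-fold and is again rated NCS.

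- Descriptive statistics: included, and perhaps visible as the maximum.
- Shift table: NCS→NCS.
- Named counts: absent.
- Listing: present, with grade.
- TEAE tables: absent, because the finding is not to be recorded as an AE.

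**3. Whether the AE route closes the gap.** The SAP tabulates TEAEs by maximum CTCAE grade, and a TEAE includes worsening in severity (SAP VII.B). A laboratory value must pass these filters to get there:

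- *Judgement.* It must be called clinically significant or meet another recording criterion in Protocol 8.3.7, such as symptoms or need for intervention.
- *Definition.* Protocol 8.2.7 ties clinical significance to findings unrelated to HFrEF or another pre-existing condition, unless judged worse than expected. Subjects abnormal at baseline are therefore the ones most easily left as NCS.
- *Time.* From 30 days after dosing, only SAEs at least possibly related to study drug or procedures are collected (Protocol 8.3.3; SAP VII.B).

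Protocol Table 14 shows how much testing falls after that limit:

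- Chemistry after dosing: Days 2, 7, 15, 30, 60, 90, 135 and 180, so 8 visits, of which 4 (Days 60, 90, 135, 180) come after Day 30.
- Hematology: the same visits plus Day 3, so 9 visits, of which 4 come after Day 30.

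At those 4 visits, a non-serious grade rise cannot enter the TEAE tables even if the investigator calls it clinically significant.

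**4. Whether the SAP declares a change.** Its Changes from Protocol section addresses the same 9.4.3 sentence and drops only the abnormal vital-sign summary. It says nothing about laboratory values.

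**5. Weight of one subject.** Counting the sentinel, an unexpanded cohort has 1 + 3 = 4 JK07 subjects and an expanded one has 1 + 6 = 7. One uncounted subject is 1/4 = 25% or 1/7 ≈ 14% of the dose group.

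**The case against.** The strongest reply is that most of the information is already in the plan. The primary laboratory endpoint is change from baseline, and SAP VII.C delivers it with minimum and maximum; in a group of 4, a several-fold rise would probably show as the maximum. Every result is listed with its grade, and listings this short can be read. Protocol 9.4.3 does not promise a graded table, and normal-to-abnormal counts are an ordinary reading of its words. The study is descriptive: "Formal statistical hypothesis testing is not planned for this study", and "no prospective calculations of statistical power have been made", so no error rate or power is affected. SAP VII also says that categorical safety data are summarized by count and percentage, and the table shells are a separate document not reviewed here.

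Much of this stands, and it rules out stronger readings that a reader might infer:

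- *That severe worsening from an abnormal baseline is counted nowhere.* Not supported. Through Day 30, worsening judged clinically significant and recorded as an AE is tabulated by maximum grade. It may also be a DLAE, and the DRC can name other abnormalities as DLAEs. A full three-level shift table would show NCS→CS.
- *That the laboratory promise was dropped.* Not supported. The normal-to-abnormal counts deliver part of it.
- *That CPK or eGFR illustrates the gap.* CPK is summarized as a biomarker under SAP X, and eGFR is not an analyte in Protocol Table 13.

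The reply does not supply the missing count. A maximum does not say how many subjects rose by a grade or reached Grade 3, and a listing is not an incidence. The general sentence in SAP VII names no laboratory grade and no comparison with baseline.

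**Conclusion.** The point holds in a limited form. SAP VII.C names CTCAE laboratory grades only in a listing, and a grade rise from an abnormal baseline that stays within NCS or within CS is in no laboratory count. It reaches a graded table only if the investigator calls it clinically significant and records it as an AE by Day 30 or, after that, if it is an at least possibly related SAE. The incidence promised in Protocol 9.4.3 is partly delivered, and the SAP does not declare the shortfall.

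The size can be stated only structurally: 4 of 9 shift cells are in the named counts, and 4 of 8 post-dose chemistry visits fall after non-serious AE collection ends. The documents do not say how often baselines are abnormal, so no share of affected subjects is claimed. The conclusion assumes that the table shells add no grade table beyond the SAP text. This is an inexpensive improvement to the safety tables, not a failure of the primary endpoint.

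**What to change.** In SAP VII.C:

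1. Define a treatment-emergent laboratory abnormality as a post-baseline CTCAE grade above the baseline grade.
2. For each gradable analyte, tabulate baseline grade against worst post-baseline grade, by JK07 dose and pooled placebo, through Day 15 and through Day 180.
3. In the same table, give the number of subjects rising at least one grade and the number reaching Grade 3 or more. The denominator is subjects with a baseline and at least one post-baseline value.
4. For analytes that cannot be graded, use low/normal/high against the reference range.
5. Keep the investigator's Normal/CS/NCS shift as supportive.

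If the table is not added, record the omission in the SAP's Changes from Protocol section.

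The cost is one more table, built from grades the SAP already derives. Data collection and study conduct do not change.
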